2.3.2 Study design for subjects with erythrodermic PSO or generalized pustular PSO

2.3.2.1 Period 1: Screening

The Screening Period of 2 to 5 weeks will be used to confirm eligibility and obtain laboratory data.

2.3.2.2 Period 2: Initial Period - Week 0 to Week 16

At least 10 subjects in the cohort with erythrodermic PSO or generalized pustular PSO will be allocated in a 1:1 ratio to the following open-label study treatments:

- CZP 400mg (n ≥ 5): CZP administered sc at the dose of CZP 400mg Q2W
- CZP 200mg (n ≥ 5): CZP administered sc at the dose of CZP 400mg at Weeks 0, 2, and 4, followed by CZP 200mg Q2W (starting at Week 6)

2.3.2.3 Period 3: Maintenance Period - Week 16 to Week 52

The treatment received in Period 3 will be based on the initial study treatment and on response to open-label treatment at Week 16:

- Subjects achieving a “much improved” or “very much improved” in the Global Improvement Score (for subjects with generalized pustular PSO) or a PASI50 response (for subjects with erythrodermic PSO) will continue to receive the same treatment as randomized.
- Subjects in the CZP 200mg Q2W group who are not in response (not achieving “much improved” or “very much improved” in the Global Improvement Score [for subjects with generalized pustular PSO] or a PASI50 response [for subjects with erythrodermic PSO]) will be allowed to have their dose increased to CZP 400mg Q2W, at the discretion of the Investigator. Subjects randomized to CZP 400mg Q2W will continue to receive CZP 400mg Q2W at the discretion of the Investigator. If, in the opinion of the Investigator, the subject is not receiving benefit at the 400mg Q2W dose, the subject could be withdrawn from the study. Per the Withdrawal Criteria, subjects who develop an aggravation of the primary disease or concomitant disease with hospitalization in the opinion of the Investigator must be withdrawn from the study.

2.3.2.4 Period 4: Safety Follow-up: Week 52 to Week 60

All subjects, including those withdrawn from study treatment, will have a Safety Follow-Up Visit, 10 weeks after their final dose of study medication.

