3.6 Treatment assignment and treatment groups

All safety analyses and pharmacokinetic analyses will be based on actual treatment assignment, whereas all efficacy analyses will be based on randomized treatment assignment, unless specified otherwise. Analyses for escapers will be based on Escape Maintenance Treatment Group or on the latest dose of study medication the subject received before escape.

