3.6.2 Subjects with erythrodermic PSO or generalized pustular PSO

Period 2 – Initial Period - Week 0 to Week 16

Efficacy and Safety Evaluations:

Efficacy and Safety data will be presented by the following randomized treatment groups:

- Erythrodermic PSO CZP 200mg Q2W
- Erythrodermic PSO CZP 400mg Q2W
- Erythrodermic PSO All CZP (only for safety data)
- Generalized Pustular PSO CZP 200mg Q2W
- Generalized Pustular PSO CZP 400mg Q2W
- Generalized Pustular PSO All CZP (only for safety data)
- All Subjects (only for safety data)

Selected parameters (where stated in the following sections) may be summarized by treatment group and subgroup (Definition of subgroups, see [Section 4.8](#)).

Period 3 – Maintenance Period - Week 16 to Week 52

Efficacy Evaluations:

During the 36-week Period 3, subjects will be allocated to dose groups based on their Week 16 PASI50 response/Global Improvement Score, as appropriate based on PSO type, and whether or not the subject ever up-titrated their dose during the Maintenance Period. Efficacy data will be summarized based on the following maintenance treatment groups:

- Erythrodermic PSO CZP 200mg Q2W/CZP 200mg Q2W – includes subjects who remained on CZP 200mg Q2W for the duration of both periods
- Erythrodermic PSO CZP 400mg Q2W/CZP 400mg Q2W – includes subjects who remained on CZP 400mg Q2W for the duration of both periods
- Erythrodermic PSO CZP 200mg Q2W/CZP 400mg Q2W – includes subjects who up-titrated to CZP 400mg Q2W at any point during the Maintenance Period
- Generalized Pustular PSO CZP 200mg Q2W/CZP 200mg Q2W – includes subjects who remained on CZP 200mg Q2W for the duration of both periods

- Generalized Pustular PSO CZP 400mg Q2W/CZP 400mg Q2W – includes subjects who remained on CZP 400mg Q2W for the duration of both periods
- Generalized Pustular PSO CZP 200mg Q2W/CZP 400mg Q2W – includes subjects who up-titrated to CZP 400mg Q2W at any point during the Maintenance Period

Safety Evaluations:

For safety analysis, data of the Combined Initial and Maintenance Period will be summarized using the same treatment groups as listed for the Initial Period. Additionally, all Generalized Pustular PSO, all Erythrodermic PSO and all subjects will be summarized.

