8.3.18 Global Improvement Score for Pustular PSO

The analysis will be based on the Generalized Pustular PSO Set (GPPS). The Global Improvement Score is evaluated by the Investigators as “very much improved,” “much improved,” “minimally improved,” “no change,” or “worsened” based on changes from the baseline JDA severity index scores and components, as presented in [Table 8-6](#).

Table 8–6: Global Improvement Score

	Change in JDA Severity Classification Score		Other criteria
Very much improved	Reduction by ≥ 3 points	or	Clear or almost clear of signs of generalized pustular PSO
Much improved	Reduction of 1 or 2 points	or	At least 1 of the following: Erythema area with pustules (%) reduced by $\leq 30\%$ compared to Baseline Clinically meaningful improvement in at least 2 other components of the JDA Severity Index for generalized pustular PSO (erythema area, edema area, WBC, CRP, albumin)
Minimally improved	0 points (no change)	and	At least 1 of the following: Erythema area with pustules (%) reduced by $\leq 20\%$ compared to Baseline Clinically meaningful improvement in at least 1 other component of the JDA Severity Index for generalized pustular PSO (erythema area, edema area, WBC, CRP, albumin)
No change	0 points (no change)	and	Not meeting the other criteria of minimally improved
Worsened	$\geq +1$ point	-	Not applicable

Frequency tables by visit and by randomized treatment group for the Initial Period as well as by visit and by maintenance treatment group for the Maintenance Period will be provided for the results of the Global Improvement Score based on the GPPS on Observed case data and NRI imputed data.

Within NRI imputation, missing values are imputed with the category “No Change”.

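### Cohort maintenance efficacy is grouped by whether a subject ever up-titrates (SAP 3.6.2), so the 200/200 column is selected on outcome and is not comparable with 400/400; summaries by randomised dose should be added

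*SAP*

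**What the plan says.** The cohort is randomised 1:1, open-label, to 200mg or 400mg Q2W (Protocol 5.1.2.2). Under SAP 2.3.2.3, a 200mg subject not in response at Week 16 "will be allowed to have their dose increased to CZP 400mg Q2W, at the discretion of the Investigator". For the other arm, "Subjects randomized to CZP 400mg Q2W will continue to receive CZP 400mg Q2W at the discretion of the Investigator", with withdrawal possible if there is no benefit.

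The general rule in SAP 3.6 is that "all efficacy analyses will be based on randomized treatment assignment, unless specified otherwise". SAP 3.6.2 specifies otherwise for the cohort's Period 3 efficacy. Groups depend on Week 16 response "and whether or not the subject ever up-titrated their dose during the Maintenance Period". Within each PSO type:

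- 200/200 "includes subjects who remained on CZP 200mg Q2W for the duration of both periods";
- 400/400 "includes subjects who remained on CZP 400mg Q2W for the duration of both periods";
- 200/400 "includes subjects who up-titrated to CZP 400mg Q2W at any point during the Maintenance Period".

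These groups carry the cohort's maintenance tables. SAP 8.3.18, for example, has frequency tables "by visit and by maintenance treatment group for the Maintenance Period will be provided for the results of the Global Improvement Score". CGI-I (8.3.17), JDA score (8.3.19), DLQI and Itch (8.3.7, 8.3.8) and the erythrodermic PASI, PGA and BSA summaries (8.3.3, 8.3.4, 8.3.6) follow the same scheme. Cohort safety keeps the Initial Period groups.

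**The concern.** Group membership is settled by an event after randomisation that signals failure and that only one arm can have. A 200mg subject who does badly and is up-titrated leaves 200/200 for the whole of Period 3, and the visits still spent on 200mg are reported under 200/400. A 400mg subject who does equally badly has no higher step and stays in 400/400 unless withdrawn.

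Nothing in SAP 4.2 counts cohort up-titration as failure. The plaque part of the same SAP handles the parallel problem differently. In the final analysis escapers, including those at Week 16, stay in their assigned column (3.5.9, 3.6.1). From escape they are non-responders, or have the escape value carried forward (4.2), and post-escape data go in separate tables.

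Efficacy in this cohort and long-term efficacy are stated objectives (Protocol 3.3), and these tables are most of the maintenance evidence for the cohort. At stake is whether a reader who compares the 200mg and 400mg columns is comparing like with like.

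**Working it through.** **No figure to reproduce.** Protocol 14.8.2 says that no sample size could be calculated for the cohort, and the documents give no expected response or up-titration rate. The check is of direction and possible size.

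**Inputs, all assumed.** p is the true response on the randomised dose; u is the share of 200mg failures who up-titrate; w is the share of 400mg failures who withdraw and leave the observed-case denominator. Response is taken to be the same criterion that triggers up-titration.

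**Formulas.**
- 200/200 shows p / (p + (1−p)(1−u))
- 400/400 shows p / (p + (1−p)(1−w))

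For p = 0.6, u = 0.5: 0.6 / (0.6 + 0.4 × 0.5) = 0.6 / 0.8 = 75%.

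**Equal true response in both arms, no 400mg withdrawals (w = 0).**

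| p | 200/200, u = 0.5 | 200/200, u = 1 | 400/400 |
|---|---|---|---|
| 0.4 | 57% | 100% | 40% |
| 0.6 | 75% | 100% | 60% |
| 0.8 | 89% | 100% | 80% |

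The gap in favour of 200mg is 9 to 60 percentage points in these cases, and zero if nobody up-titrates.

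**Truly worse 200mg dose (40% against 80%, w = 0).** With u = 0.5 the display is 57% against 80%; with u = 1 it is 100% against 80%, so the ranking can reverse.

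**Withdrawal of 400mg failures (p = 0.6, u = 0.5, observed case).** w = 0 gives 75% against 60%; w = 0.5 gives 75% against 75%; w = 1 gives 75% against 100%. The gap closes when w = u and reverses when w exceeds u.

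**Scale of the actual display.** The minimum of 10 subjects, split over two doses and two PSO types, averages 10/4 = 2.5 per cell. In an illustrative cell of three with two responders, moving the one failure to 200/400 turns 2/3 into 2/2.

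**Visits before the switch.** Dosing follows all other assessments at a visit (SAP Table 13–1, footnote l). At the Week 16 assessment, therefore, no cohort subject has yet switched. The erythrodermic PGA and BSA maintenance summaries include Week 16 (8.3.4, 8.3.6). One report can thus give two different 200mg results for that visit: by randomised dose in the Initial Period table, and by 200/200 in the maintenance table.

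**Interim against final.** The interim maintenance analysis stops at Week 24 (Table 8–4, footnote). A subject who up-titrates later would sit in 200/200 at the interim and in 200/400 at the final, which changes the Week 16 to 24 columns with no new data at those visits.

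**The case against.** Several counter-arguments have force.

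- *Exploratory cohort.* Protocol section 2 calls the evaluation exploratory. There is no primary or secondary cohort variable (4.1.1, 4.1.2) and no between-dose test, and the optimal-dose objective (3.2) concerns plaque PSO only. This stands, and it limits the consequence to how descriptive tables read.
- *400mg failures can leave.* They may be withdrawn, so a reader who infers that all of them stay in 400/400, or that 200mg is always flattered, goes further than the documents. This stands for observed-case tables. In the imputed CGI-I and Global Improvement Score tables a missing value becomes 'No Change' (8.3.17, 8.3.18), so the offset should not arise there if withdrawn subjects are kept in 400/400. Read literally, the group definitions give withdrawn subjects of either dose no group, so the SAP leaves this open.
- *The formula is a special case.* Up-titration depends on PASI50 or on the Global Improvement Score. PASI75/90/100, PGA, DLQI, Itch and JDA are different measures, so 100% in 200/200 would not follow for them. This stands.
- *Pooled examples mislead.* A reader might picture five per dose shown as 3/3 against 3/5. No such display is planned, because every efficacy column is split by PSO type.
- *Timing.* Protocol 5.1.2.3 and SAP 2.3.2.3 tie the decision to Week 16 response. For subjects up-titrated then, membership is fixed at the start of Period 3. SAP 3.6.2 and 10.1.2 nevertheless provide for later up-titration, and the Week 16 selection remains in either case.
- *Already visible.* 200/400 has its own column, the CGI-I line plot is by randomised dose, and so is the PASI percent-change plot in 8.3.3 (population not stated). Re-pooling 200/200 with 200/400 would still mix data from before and after the switch without a failure rule.
- *Deliberate choice.* SAP 12.2 records that the 200/400 definition was added on purpose, and description by regimen is legitimate. Cohort up-titration is also optional, unlike plaque escape. This supports keeping the groups, not relying on them alone.

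**Conclusion.** The concern holds in limited form. The 200/200 column is selected on outcome and is not comparable with 400/400, even at the Week 16 assessment before anyone has switched. The tendency is to favour 200mg. The size depends on how many 200mg failures are up-titrated, which is discretionary and not stated. Under equal true response, with half to all failures up-titrated and no 400mg withdrawals, it is 9 to 60 points on the trigger endpoint. It is smaller or reversed in observed-case tables if 400mg failures withdraw as often or more often.

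A reader might infer that the plan biases a dose comparison or a trial conclusion. The documents do not support that: the cohort analysis is descriptive, no test between doses is planned, and the plaque primary analysis is untouched. With two or three subjects per cell at the minimum size, the percentages show direction only. This is a worthwhile and cheap improvement to the presentation.

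**What to change.** In SAP 3.6.2, add cohort maintenance summaries by randomised dose within PSO type, keeping all randomised subjects in the CFAS, including those later withdrawn. For subjects who up-titrate:

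- show data as observed up to and including the up-titration visit;
- after it, count binary responses as non-response;
- for continuous and ordered-category variables, including CGI-I and the Global Improvement Score, carry forward the value at up-titration. A favourable category at that visit counts as non-response, and a 'worsened' rating is not replaced by 'No Change';
- show data after up-titration separately.

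Keep 200/200, 200/400 and 400/400 as supplementary descriptions by regimen, labelled as outcome-dependent, and state where withdrawn subjects are counted.

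The cost is SAP wording and some extra descriptive tables for a small cohort. No new data are needed and clinical management does not change. The 200mg figures may look less favourable than under the present grouping.

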3.7 Center pooling strategy

All results will be summarized across centers and will not be stratified by center. There will be no specific pooling strategy.

3.8 Coding dictionaries

All AEs, concomitant diseases, and medical history will be coded for analysis according to the Medical Dictionary for Regulatory Activities (MedDRA)[®] coding dictionary, version 18.1 or higher. Prior and concomitant medications will be coded for analysis using the World Health Organization Drug dictionary (WHO-DD), version SEP/2015. As the dictionary version may change during the course of a study, the actual version of coding dictionaries in use at the end of this study will be identified on the table.

3.9 Changes to protocol-defined analyses

The definitions of the Analysis Sets have been clarified.

4 STATISTICAL/ANALYTICAL ISSUES

4.1 Adjustments for covariates

For the analysis of the primary, secondary and other key efficacy endpoints (PASI50, e.g. PASI100), prior biologic exposure (yes/no) will be included as factor in the statistical model. Prior biologic exposure is a stratification variable used in the randomization and is included in the analysis as this may have an impact on the efficacy of treatment. The analysis of the secondary endpoints DLQI score at Week 16 and Itch Numeric Rating Scale at Week 16 will include prior biologic exposure as well as the Baseline score as a covariate. Inclusion of the Baseline score will account for any potential Baseline imbalance.

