7.10 Randomization and numbering of subjects

An IRT will be used for assigning eligible subjects to a treatment regimen (as applicable) based on a predetermined production randomization and/or packaging schedule provided by UCB (or designee). The randomization schedule will be produced by the IRT vendor. Subject treatment assignment will be stratified by prior biologic exposure (yes/no) and psoriatic arthritis (yes/no).

The IRT will generate individual assignments for subject kits of IMP, as appropriate, according to the visit schedule.

To enroll a subject (Visit 1), the Investigator or designee will contact the IRT and provide brief details about the subject to be enrolled. Each subject will receive a 5-digit number assigned at screening that serves as the subject identifier throughout the study. The subject number will be required in all communication between the Investigator or designee and the IRT regarding a particular subject. Subject numbers and kit numbers will be tracked via the IRT.

To randomize a subject, the Investigator or designee will contact the IRT and provide brief details about the subject to be randomized. The IRT will automatically inform the Investigator or designee of the subject's randomization number. The IRT will allocate kit numbers to the subject based on the subject number during the course of the study. The randomization number must be incorporated into the CRF.

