14.2 General statistical considerations

The primary efficacy variable will be analyzed for subjects with moderate to severe chronic plaque PSO in the FAS. In order to verify the robustness of the efficacy results, primary efficacy variables in the primary analysis will also be analyzed for the PPS as sensitivity analysis.

The statistical analysis of the primary and secondary efficacy variables will account for multiplicity by using a fixed sequence testing procedure. As these variables will be evaluated for both doses of CZP, the statistical analysis for each dose will be carried out in separation of one another. To account for the testing of multiple doses, the alpha level of 0.05 will be split evenly between CZP 400mg Q2W and CZP 200mg Q2W so that each dose is evaluated at an alpha level of 0.025.

Within each dose, the primary endpoints of PASI75 at Week 16 will be evaluated first. Statistical testing of PGA (clear or almost clear) response at Week 16 will be performed only if primary endpoint (PASI75) is significant at the 0.025 alpha level for a given dose.

Similarly, testing of PASI90 at Week 16 will be performed only if primary endpoint (PASI75) and PGA are significant at the 0.025 level, and similarly, testing of change from Baseline in DLQI at Week 16 will be performed only if PASI75, PGA, and PASI90 are significant at the 0.025 level.

Table 14–1 outlines the testing procedure.

Table 14–1: Statistical testing procedure

CZP 200mg Q2W vs Placebo	CZP 400mg Q2W vs Placebo
1. PASI75 response at Week 16	1. PASI75 response at Week 16
2. PGA response at Week 16	2. PGA response at Week 16
3. PASI90 response at Week 16	3. PASI90 response at Week 16
4. Change from Baseline in DLQI at Week 16	4. Change from Baseline in DLQI at Week 16

CZP=certolizumab pegol; DLQI=Dermatology Life Quality Index; PASI=Psoriasis Activity and Severity Index; PGA=Physician’s Global Assessment; Q2W=every 2 weeks

Note: All significance tests are performed at an alpha level of 0.025.

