14.3.2 Other efficacy analyses

14.3.2.1 Analysis of the secondary efficacy variables for subjects with moderate to severe chronic plaque PSO

The secondary efficacy variables will be analyzed for all subjects in the FAS.

Secondary efficacy variables are PASI90, PGA response, and change from Baseline in DLQI at Week 16.

A subject will be classified as a PGA responder if the PGA is Clear or Almost clear with at least a 2-category improvement relative to Baseline. The analysis of PASI90 and PGA response at Week 16 will be analyzed for treatment effects using pairwise comparisons based on the same method as that for the primary efficacy variable.

The MCMC algorithm is based on the multivariate normal model; imputed values for PGA will not generally be one of the discrete values actually used in PGA scoring (0, 1, 2, 3, or 4).

Therefore, standard rounding rules will be applied to the imputed values in order to derive the binary PGA response variable. For example, if a subject has a PGA score imputed as 1.4 (and assuming a Baseline PGA score of 3), this imputed value would be rounded down to 1, and the minimum change from Baseline of 2 would have been met. Therefore, this subject would be considered a responder.

The significance testing of each CZP treatment group vs PBO will be part of the fixed sequential testing procedure described in Section 14.2.

The analysis of DLQI will be based on the change from Baseline at Week 16. Treatment group comparisons for each CZP treatment group vs PBO will be performed using an analysis of covariance (ANCOVA) model with treatment group and prior biologic exposure (yes/no) as factors and Baseline DLQI score as a covariate. The treatment differences and corresponding 97.5% confidence intervals will be calculated based on the adjusted means. Missing values will be imputed using last observation carried forward (LOCF). Each CZP dose will be compared against PBO to establish superiority over PBO and will be tested at an alpha of 0.025 as part of the fixed sequence testing procedure described in Section 14.2.

14.3.2.2 Analysis of the other efficacy variables for subjects with moderate to severe active plaque PSO

All other efficacy variables (eg, PASI50, PASI75, PASI90, PASI100, PGA, MCID) will be analyzed for all subjects in the FAS.

All categorical variables (eg, PASI score, PGA score, BSA score, DLQI) will be summarized using frequency tables by each visit.

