4.5 Multiple comparisons/multiplicity

The statistical analysis of the primary and selected secondary efficacy variables will account for multiplicity and control the familywise type I error rate at a 2-sided alpha level of 0.05 by using a fixed sequence testing procedure. The hypotheses are mapped into 2 sets (H1, H3, H5 and H7) and (H2, H4, H6 and H8) so that hypotheses within each set correspond to the same CZP dose. The type I error will be split equally between CZP 400mg Q2W and CZP 200mg Q2W, so that each dose will be tested at a 2-sided alpha level of 0.025.

The first 2 hypotheses for each dose (H1 for CZP 400mg Q2W; H2 for CZP 200mg Q2W) test whether the given CZP dose is superior to placebo for PASI75 response at Week 16. These are the hypothesis tests corresponding to the primary endpoint. If this is rejected at a 2-sided alpha level of 0.025, that alpha will be passed to the next test in the sequence, allowing the testing procedure to proceed.

The hypotheses associated with the subsequent tests are for secondary efficacy endpoints and are based on testing for superiority relative to placebo. See Figure 4–1 for details on this procedure.

Figure 4–1: Fixed sequence testing procedure

If all hypotheses within one set of hypotheses (either CZP 400mg Q2W or CZP 200mg Q2W) have been rejected, the corresponding type I error probability can be passed on to the other set of hypotheses and that set can be retested if necessary at a 2-sided alpha level of 0.05 (Bretz et al, 2009).

All significance tests are performed at an alpha level of 0.025.

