Not relevant	0
Question unanswered	0
Q7: 'prevented work or studying' = yes	3

The DLQI is calculated by adding the score of each question and ranges from 0 to 30 with higher scores indicating lower HRQoL:

Meaning of DLQI Scores

0-1 = no effect at all on patient's life

2-5 = small effect on patient's life

6-10 = moderate effect on patient's life

11-20 = very large effect on patient's life

21-30 = extremely large effect on patient's life

A ≥ 4 -point change in the DLQI score (DLQI response) has been reported to be meaningful for the patient (within-patient minimal important difference); a DLQI absolute score of ≤ 1

indicates DLQI remission (ie, no or small impact of the disease on HRQoL) (Basra et al, 2015).

Because Question 7 (Q7) has a sub-question (referred to as Q7a here) after the leading yes/no question, some clarifying rules for scoring are provided:

- If Q7='yes', then score=3 regardless of the responses to Q7a.
- If Q7='no', 'not relevant', or is missing and Q7a='A lot', then score= 2.
- If Q7='no', 'not relevant', or is missing and Q7a='A little', then score=1.
- If Q7='no', 'not relevant', or is missing and Q7a='Not at all', then score=0.
- If Q7='no', 'not relevant', and Q7a is missing or not applicable, then score=0.
- If Q7 is missing and Q7a is missing, Q7 is considered unanswered (see below for details on how this impacts the overall DLQI score).

If 1 question is left unanswered, this is scored 0 and the scores are summed as usual. If 2 or more questions are left unanswered, the questionnaire is not scored.

The analysis of DLQI will be based on the change from Baseline at Week 16 for the FAS. Treatment group comparisons for each CZP treatment group vs placebo will be performed using an analysis of covariance (ANCOVA) model with treatment group and prior biologic exposure as factors and Baseline DLQI score as a covariate. The least squares (LS) means and standard errors derived from the model will be presented for each treatment group. Additionally, adjusted mean treatment differences, corresponding confidence intervals, and p-values will be reported. Missing values will be imputed using LOCF. Each CZP dose will be compared against placebo to establish superiority over placebo and will be tested at a significance level of 0.025 as part of the fixed sequence testing procedure outlined in [Section 4.5](#).

8.2.4 Change from Baseline in Itch Numeric Rating Scale at Week 16

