The Itch Numeric Rating Scale has been developed as a simple, single item instrument to assess the patient-reported severity of itch at its greatest intensity during the past 24h period. Subjects indicate itch severity by circling the integer that best describes the worst level of itching due to PSO in the past 24h period on an 11-point scale anchored at 0, representing "no itching" and 10, representing "worst itch imaginable" (Kimball et al, 2016).

Descriptive statistics for observed and change from baseline in Itch Numeric Rating Scale at Week 16 values will be presented for the FAS. Treatment group comparisons for each CZP treatment group vs placebo will be performed using an analysis of covariance (ANCOVA) model with treatment group and prior biologic exposure as factors and Baseline Itch Numeric Rating scale as a covariate. The least squares (LS) means and standard errors derived from the model will be presented for each treatment group. Additionally, adjusted mean treatment differences, corresponding 95% confidence intervals, and p-values will be reported. Missing values will be imputed using LOCF.

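### The Week 16 DLQI and Itch ANCOVAs omit psoriatic arthritis, one of the two randomisation strata; if it is prognostic, their standard errors are somewhat too large and the DLQI test is slightly conservative

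*SAP*

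**What the plan says.** Protocol 7.10 names two stratification factors: "Subject treatment assignment will be stratified by prior biologic exposure (yes/no) and psoriatic arthritis (yes/no". SAP 2 repeats them.

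The models for the two continuous secondary endpoints carry only one. SAP 4.1 states: "DLQI score at Week 16 and Itch Numeric Rating Scale at Week 16 will include prior biologic exposure as well as the Baseline score". SAP 8.2.3 specifies for DLQI an "analysis of covariance (ANCOVA) model with treatment group and prior biologic exposure as factors and Baseline DLQI score as a covariate", and Protocol 14.3.2.1 has the same terms: "model with treatment group and prior biologic exposure (yes/no) as factors and Baseline DLQI score as a covariate". SAP 8.2.4 uses the equivalent model for Itch, with the Baseline Itch score. SAP 8.3.7 repeats the DLQI ANCOVA for the by-visit analysis and plots adjusted means through Week 16.

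DLQI is the last of four steps for each dose: "testing of change from Baseline in DLQI at Week 16 will be performed only if PASI75, PGA, and PASI90 are significant" (Protocol 14.2). SAP 4.5 limits the procedure to part of the secondary list ("the primary and selected secondary efficacy variables will account for multiplicity"). Itch has no place in it and is reported with "corresponding 95% confidence intervals, and p-values will be reported" (SAP 8.2.4).

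In the overall plaque population, PsA otherwise appears as a descriptive subgroup for PASI75, PASI90 and PGA (SAP 4.8, 8.1.3, 8.2). DLQI and Itch have no PsA breakdown.

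**The concern.** Stratifying on a factor balances it between arms, so it no longer adds to the true variability of the treatment contrast. A linear model that leaves the factor out still counts its variance as residual error. The reported standard error then exceeds the real sampling variability, confidence intervals are wider than needed and the test rejects too rarely.

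For DLQI the stake is some power at a formally tested step. It extends a little beyond that step: under SAP 4.5 one dose passes its alpha to the other only when its whole set is rejected, so a missed DLQI result also blocks the retest of the other dose at 0.05. For Itch the stake is only the width of the 95% interval.

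**Working it through.** **Stated power.** The only power statement is for PASI75 (Protocol 14.8.1): at least 98% with 43 and 22 subjects, and above 99% with 50 and 25, at two-sided 0.025. For 70% against 15%, Fisher's exact test gives 98.6% and 99.3%, so both statements reproduce. No power is stated for DLQI or Itch.

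**Inputs from the documents.** 125 subjects, 2:2:1 (50/50/25), four strata, two-sided alpha 0.025 per dose.

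**Assumed inputs.**
- PsA share *p*: 15% and 30%. Protocol 2 cites PsA in about 30% of psoriasis patients; this trial's share is not given.
- PsA effect *d*, in residual SDs after Baseline score and prior biologic exposure: 0.3, 0.5, 0.8.
- Prior biologic exposure 20%.
- Permuted blocks of 5 within strata.

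**Closed form.** Ratio of reported to true standard error = sqrt(1 + d²p(1−p)), where p(1−p) = 0.1275 at 15% and 0.21 at 30%.

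| d | p = 15% | p = 30% |
|---|---|---|
| 0.3 | sqrt(1.0115) = 1.006 | sqrt(1.0189) = 1.009 |
| 0.5 | sqrt(1.0319) = 1.016 | sqrt(1.0525) = 1.026 |
| 0.8 | sqrt(1.0816) = 1.040 | sqrt(1.1344) = 1.065 |

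**Simulation** (20,000 trials per case, one CZP arm against placebo; each cell is without / with PsA in the model):

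| p, d | Mean SE | Null rejection, % | Power, effect 0.5 SD | 0.7 SD | 1.0 SD | 1.2 SD |
|---|---|---|---|---|---|---|
| 15%, 0.5 | 0.2494 / 0.2456 | 2.35 / 2.54 | 39.9 / 41.0 | 70.7 / 71.9 | 95.9 / 96.1 | 99.3 / 99.4 |
| 15%, 0.8 | 0.2556 / 0.2457 | 1.92 / 2.44 | 37.0 / 40.5 | 68.4 / 71.5 | 95.3 / 96.0 | 99.4 / 99.6 |
| 30%, 0.5 | 0.2520 / 0.2456 | 2.10 / 2.43 | 38.9 / 41.0 | 70.1 / 72.1 | 95.7 / 96.2 | 99.4 / 99.5 |
| 30%, 0.8 | 0.2619 / 0.2457 | 1.74 / 2.38 | 34.9 / 40.6 | 66.6 / 71.7 | 94.7 / 96.1 | 99.2 / 99.4 |

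The last row gives 0.2619/0.2457 = 1.066, against 1.065 from the formula. The empirical SD of the estimate is 0.245 to 0.247 with or without PsA, so the unadjusted estimate is no noisier; only its reported standard error is too large. Without PsA, coverage of the 95% interval is 95.1 to 96.4%, which is the Itch consequence.

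**Small PsA effect (d = 0.3, p = 30%).** Take a true SE of 0.2456 and a critical value of 2.27 (t, 119 df). Omitting PsA raises the effective threshold to 2.27 × 1.0094 = 2.291. For a treatment effect of 0.5 SD, 0.5/0.2456 = 2.036 and power falls from about 40.8% to 39.9%, a loss of 0.8 points before rounding. The same calculation gives 0.7 points at 0.7 SD and 0.2 at 1.0 SD. With no PsA effect, power differs by at most 0.1 points.

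**Control.** In a separate simulation (8,000 trials, p = 30%, d = 1.0), stratified allocation gave a reported-to-true SE ratio of 1.09 and 1.70% null rejection. With PsA not stratified, these were 1.00 and 2.59%. The conservatism therefore comes from stratifying on PsA and then omitting it. Blocks of 10 gave the same picture (ratio 1.09, null rejection 1.58%).

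**The case against.** The strongest reply is that this is a covariate preference. Protocol and SAP agree on the DLQI model, the estimate is unbiased and type I error is protected. SAP 4.1 and 8.1.2 give two reasons for including prior biologic exposure: it was a stratifier and it may affect efficacy. Nothing in the documents says the second holds for PsA. The visible losses need a PsA effect of at least 0.5 SD beyond Baseline score. The largest also needs a modest treatment effect, in a trial that reaches DLQI only after three other endpoints have succeeded. Blocking is assumed; Protocol 7.10 mentions only a predetermined schedule. Finally, with interim results already known, changing the formal model is no longer clean, and a supportive analysis cannot restore power to the formal test.

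Most of this stands and limits the point. It does not remove it. The trial chose PsA as a stratifier, and adjusting for it costs one degree of freedom (120 to 119 at n = 125) and essentially nothing if PsA is irrelevant. As planned, no overall-population output would show whether PsA matters for DLQI or Itch.

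**Conclusion.** The point holds and is minor. If allocation is balanced within strata and PsA is prognostic after the planned adjustments, the DLQI and Itch standard errors are overstated by under 1% (0.3 SD), 1.6 to 2.6% (0.5 SD) or 4.0 to 6.6% (0.8 SD). Per-test DLQI power loss is under about 1 point at 0.3 SD and at most 1.4 points for treatment effects of 1.0 SD or more. Within the range examined it reaches about 5 to 6 points only with a 0.8 SD PsA effect, 30% PsA and a treatment effect of 0.5 to 0.7 SD. If PsA is not prognostic, nothing is lost.

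Three stronger readings are not supported.
- A reader might infer that the DLQI test is invalid or its estimate biased. The error runs the other way: null rejection is at or below nominal.
- A reader might infer that the plan contradicts itself. It does not, because its stated rationale for the included factor has a second condition that it never asserts for PsA.
- A reader might extend the loss to PASI75, PASI90 and PGA, whose models also omit PsA. The residual-variance argument belongs to linear models and does not carry over directly to logistic regression.

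**What to change.** Before unblinding, the change would have been to add PsA (yes/no) as a factor to both ANCOVAs. That time appears to have passed. SAP 4.3 releases treatment codes to sponsor personnel after the Week 24 lock, Table 8-4 includes the secondary endpoints in the interim analysis, SAP 9.3 reports interim results, and SAP 12.2 describes the interim analysis as done.

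So keep the pre-specified ANCOVAs as the formal analyses. In SAP 4.1, 8.2.3, 8.2.4 and 8.3.7, add PsA-adjusted versions labelled as supportive. Include 8.3.7 so that the by-visit DLQI output handles Week 16 in the same way as 8.2.3. Define PsA as the stratum recorded in the IRT at randomisation, because SAP 6.2 takes Baseline PsA from the eCRF. List the DLQI addition in SAP 3.9, since Protocol 14.3.2.1 specifies that model without PsA.

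The cost is wording in four SAP sections, one entry in 3.9, a few extra model runs and one degree of freedom; the factor is already held. The supportive models give correctly sized standard errors and intervals, but they do not restore power to the alpha-controlled DLQI test. The logistic models need no change on this account.
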